## 7. STATISTICAL METHODS AND DETERMINATION OF SAMPLE SIZE

### 7.1 STATISTICAL DESIGN – MODEL

The trial will be performed as an open-label trial. The objective of the design is to determine the MTD defined as the highest dose with less than 25% risk of the true DLT rate being equal or above 0.33 (EWOC criterion). The phase I dose-finding will be guided by a Bayesian 2-parameter logistic regression model with overdose control ([R13-4806](#); [R13-4803](#)).

The model is given as follows:

$$\text{logit}(\pi_d) = \log(\alpha) + \beta * \log(d/d^*),$$

where  $\text{logit}(\pi) = \log(\pi/(1-\pi))$ .

$\pi_d$  represents the probability of having a DLT in the MTD evaluation period at dose  $d$ ,  $d^* = 8$  mg is the reference dose, allowing for the interpretation of  $\alpha$  as the odds of a DLT at dose  $d^*$ , and  $\theta = (\log(\alpha), \log(\beta))$  with  $\alpha, \beta > 0$  is the parameter vector of the model. The estimated probability of a DLT at each dose level from the model will be summarized using the following intervals:

Under toxicity: [0.00, 0.16)

Targeted toxicity: [0.16, 0.33)

Over toxicity: [0.33, 1.00]

The BLRM-recommended dose for the next cohort is the level with the highest posterior probability of the DLT rate falling in the target interval [0.16, 0.33) among the doses fulfilling EWOC. Applying the EWOC criterion, it should be unlikely (<25% posterior probability) that the DLT rate at that dose will exceed 0.33. However, the maximum allowable dose increment for the subsequent cohort will be no more than 50 % for each dose level.

The MTD may be considered reached if one of the following criteria is fulfilled:

1. The posterior probability of the true DLT rate in the target interval [0.16 – 0.33) of the MTD is above 0.5, OR
2. At least 12 patients have been treated in the dose escalation phase of the trial, of which at least 6 at the MTD.

The SMC may recommend stopping the dose escalation phase after the criterion for MTD is fulfilled. Further patients may be included to confirm this MTD estimate. If no DLT is observed at a dose of which the efficacy is considered sufficient, the SMC may decide to include an additional number of patients at this dose level and to declare this dose as the dose recommended for further testing

Since a Bayesian approach is applied, a prior distribution  $f(\theta)$  for the unknown parameter vector  $\theta$  needs to be specified.

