3. A low-toxicity weakly informative prior was derived reflecting the case that the compound would be much less toxic than expected. For this prior component, it was assumed that the median DLT rate at 2 mg would equal 0.005, and the median DLT at the anticipated MTD of 8 mg would equal 0.1. These assumptions yield  $\mu_3 = (-2.20, 0.80)$ , i.e. basically a flat curve. The standard deviations and correlations were set to  $\sigma_{3,11} = 2$ ,  $\sigma_{3,22} = 1$ . The correlation was set to 0, i.e.  $\rho_3 = 0$ . The prior weight  $a_3$  for the third component was chosen as 0.1.

A summary of the prior distribution is provided in Table 7.1:2. Additionally, the prior probabilities of DLTs at different doses, as well as the corresponding probability of under-, targeted and over toxicity, are shown in Table 7.1:3. Graphically, the prior medians with accompanying 95% credible intervals are shown in [Figure 7.1:1](#). As can be seen from both, the table and the figure, the prior medians of the DLT probabilities are in-line with the prior medians derived from the weakly informative prior, and the uncertainty around the medians is large, showing the low amount of information this prior provides. This is also supported by the prior sample size, i.e. the information contained in the prior. This is approximately equal to 2.8 patients at 4 mg. A detailed evaluation of the model using hypothetical data scenarios and operating characteristics is provided in the statistical [Appendix 10.2](#).

Table 7.1:2 Summary of prior distribution

[figure not shown]
Prior Component	Mixture Weight	Mean Vector	SD Vector	Correlation
1: MAP prior	0.800	(-0.94, 0.61)	(0.91,0.91)	-0.08
2: High Tox.	0.100	(0.85,0.79)	(2,1)	0
3: Low Tox.	0.100	(-2.20,0.80)	(2,1)	0

Table 7.1:3 Prior probabilities of DLTs at selected doses

Dose	Probability of true DLT rate in			Quantiles				
	[0-0.16)	[0.16-0.33)	[0.33-1)	Mean	SD	2.5%	50%	97.5%
4 mg	0.682	0.189	0.128	0.147	0.182	0.000	0.081	0.688
6 mg	0.492	0.274	0.233	0.224	0.205	0.003	0.164	0.804
7 mg	0.370	0.320	0.310	0.272	0.213	0.012	0.218	0.853
8 mg	0.248	0.330	0.422	0.329	0.220	0.024	0.285	0.897

Figure 7.1:1

Prior medians and 95% credible intervals

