## 10.2 STATISTICAL APPENDIX INCLUDING MODEL PERFORMANCE AND DATA SCENARIOS

A Bayesian logistic regression model with overdose control will be used to guide dose escalation in this trial. The BLRM is introduced in [Section 7.1](#), which also specifies the prior for the model. After patients in each cohort have completed at least one cycle of treatment, the prior distribution will be updated through Gibbs sampling procedures with the accumulated DLT data from the MTD evaluation period. Posterior probabilities for the rate of DLTs will be summarised from BLRM. Selection of the next dose will be based on these probabilities as well as on other safety and laboratory data.

The purpose of this statistical appendix is to present performance metrics (operating characteristics) that illustrate the precision of the design in estimating the MTD under various dose-toxicity relationships through computer simulation. These results are summarized in [Table 10.2:3](#). In addition, recommendations of the next dose level by the BLRM with overdose control principle are also provided under various hypothetical outcome scenarios in early cohorts to show how it facilitates on-trial dose-escalation decisions (see [Table 10.2:1](#)). For simplicity reasons, a cohort size of 3 patients who are all evaluable is assumed.

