Proprietary confidential information © 2020 Boehringer Ingelheim International GmbH or one or more of its affiliated companies

cohort or claiming 7 mg as MTD according to BLRM. Scenario 26 illustrates a case when we can claim 7 mg as MTD according to BLRM.

Scenarios 27, 28, 30 and 31 are the cases that no DLT out of 3 patients in 4mg cohort and one DLT in 6 patients in 6 mg cohort, BLRM recommends 7 mg to be tested next. In scenarios 27 and 29, the next optimal dose, i.e. the dose with the highest probability of being in the target interval, is 8 mg. In scenarios 28, the next optimal dose, i.e. the dose with the highest probability of being in the target interval, is 7 mg. Scenario 30 illustrates a case when we can claim 7 mg as MTD according to BLRM. Scenario 31 illustrates a case when we can claim 6 mg as MTD according to BLRM.

Scenarios 32 to 36 are the cases that 1 DLT out of 6 patients in 4mg cohort, no DLT in 3 patients in 6 mg cohort and no DLT in 3 patients in 7 mg cohort BLRM recommends 8 mg to be tested next.

Scenarios 37 to 41 are the cases that 1 DLT out of 6 patients in 4mg cohort, no DLT in 3 patients in 6 mg cohort and one DLT in 6 patients in 7 mg cohort BLRM recommends 8 mg to be tested next.

Scenarios 42 to 46 are the cases that no DLT out of 3 patients in 4mg cohort, one DLT in 6 patients in 6 mg cohort and no DLT in 3 patients in 7 mg cohort BLRM recommends 8 mg to be tested next.

Table 10.2:1 Hypothetical data scenarios

Scenario	Dose (mg)	# Patients	# DLT	Current Dose : P (OD)	Next recommended dose *	Next dose:		
						P (UD)	P (TD)	P (OD)
1	4 mg	3	0	0.026	6 mg [7 mg]	0.636 [0.486]	0.270 [0.339]	0.095 [0.175]
2	4 mg	3	1	0.194	4 mg	0.442	0.365	0.194
3	4 mg	3	2	0.569	NA			
4	4 mg	6	1	0.065	6 mg	0.309	0.459	0.233
5	4 mg	6	2	0.249	4 mg	0.273	0.478	0.249
6	4 mg	3	0					
	6 mg	3	0	0.027	8 mg	0.440	0.375	0.185
7	4 mg	3	0					
	6 mg	3	1	0.153	6 mg	0.427	0.420	0.153
8	4 mg	3	0					
	6 mg	6	1	0.049	7 mg	0.377	0.480	0.143
9	4 mg	3	0			0.304	0.518	0.178
	6 mg	6	2	0.178	6 mg			

Table 10.2:1 Hypothetical data scenarios (cont.)

10	4 mg 6 mg	3 6	0 3	0.397	4 mg	0.484	0.400	0.116
11	4 mg 6 mg	3 6	0 4	0.658	4 mg	0.318	0.449	0.233
12	4 mg 6 mg	6 3	1 0	0.096	7 mg	0.335	0.474	0.192
13	4 mg 6 mg	6 3	1 1	0.243	6 mg	0.215	0.542	0.243
14	4 mg 6 mg	6 6	1 1	0.125	7 mg	0.212	0.553	0.235
15	4 mg 6 mg	6 6	1 2	0.288	4 mg	0.504	0.424	0.072
16	4 mg 6 mg 8 mg	3 3 3	0 0 0	0.058	8 mg	0.604	0.338	0.058
17	4 mg 6 mg 8 mg	3 3 3	0 0 1	0.234	8 mg	0.281	0.485	0.234

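### Scenario 13 of Table 10.2:1 keeps 6 mg with a printed overdose probability of 0.243, but the Section 7.1 model gives 0.259, above the EWOC limit; scenarios 41 and 38 do not follow the stated next-dose rule

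*Protocol*

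**What the plan says.** Protocol Section 7.1 specifies the model completely: a two-parameter logistic curve with reference dose 8 mg and a three-component normal mixture prior (Table 7.1:2). The limit on the recommended dose is numeric: "Applying the EWOC criterion, it should be unlikely (<25% posterior probability) that the DLT rate at that dose will exceed 0.33". Among the doses that pass, the choice is also explicit: "The BLRM-recommended dose for the next cohort is the level with the highest posterior probability of the DLT rate falling in the target interval". That interval runs from 0.16 to just below 0.33.

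Section 10.2 says how the posterior is obtained on trial: "the prior distribution will be updated through Gibbs sampling procedures with the accumulated DLT data from the MTD evaluation period". It adds that R and JAGS were used for the scenarios and simulations. No number of draws, Monte Carlo error or convergence check appears in the protocol or the SAP.

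Three rows of "Table 10.2:1 Hypothetical data scenarios" matter here:

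- **Scenario 13** (4 mg 1/6, 6 mg 1/3): P(overdose) at 6 mg 0.243; next dose 6 mg, with under/target/over probabilities 0.215/0.542/0.243.
- **Scenario 41** (4 mg 1/6, 6 mg 0/3, 7 mg 1/6, 8 mg 2/6): next dose 8 mg, target 0.625, over 0.236.
- **Scenario 38** (as 41, but 8 mg 1/3): next dose 8 mg, target 0.597, over 0.226.

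**The concern.** Because prior, likelihood and cut-offs are all printed, each row with legible data has one correct answer. Row 13 matters because its printed value lies just under the limit, where a small numerical error decides whether a dose is available. The outcome is not exotic: it needs two DLTs in nine patients. Values close to 0.25 are also ordinary for this design, for example 0.249 in scenario 5 and 0.234 in scenario 17. If on-trial posteriors carried errors of the size seen in row 13, a dose could be recommended that the model excludes, or excluded when the model allows it.

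Rows 38 and 41 raise a different question: whether the table applies the selection rule that Section 7.1 states.

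**Working it through.** **Inputs** (protocol Section 7.1, Table 7.1:2)

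- Model: logit(π_d) = log α + β·log(d/8), with parameters (log α, log β).
- Prior: MAP component weight 0.8, mean (−0.94, 0.61), SD (0.91, 0.91), correlation −0.08; high-toxicity weight 0.1, mean (0.85, 0.79), SD (2, 1), correlation 0; low-toxicity weight 0.1, mean (−2.20, 0.80), SD (2, 1), correlation 0.
- Posterior ∝ prior × Π π_d^x (1 − π_d)^(n − x), integrated on a fine two-dimensional grid.
- P(overdose) is the posterior mass with π_d ≥ 0.33; P(target) is the mass in [0.16, 0.33).

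**Step 1: reproduce the plan's own figures.** Prior P(overdose), Table 7.1:3:

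| Dose | Printed | Recomputed |
|---|---|---|
| 4 mg | 0.128 | 0.129 |
| 6 mg | 0.233 | 0.232 |
| 7 mg | 0.310 | 0.310 |
| 8 mg | 0.422 | 0.421 |

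The model and prior are therefore read as intended.

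**Step 2: agreement across the table.** Scenarios 1–22 and 32–46 (37 rows) have readable dose-level data; 23–31 do not in the text available and were not checked. For current-dose P(overdose), the differences have both signs, a root mean square of 0.006 and a median absolute size of 0.004. Four rows differ by 0.01 or more (2, 13, 18 and 45). Scenario 5 gives 0.249 against 0.249, scenario 22 gives 0.501 against 0.501, and scenario 38 gives 0.226 against 0.226.

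**Step 3: scenario 13.** At 6 mg:

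| Input | P(overdose) |
|---|---|
| Printed in Table 10.2:1 | 0.243 |
| Grid, printed prior | 0.259 |
| Importance sampling, 8 million prior draws | 0.259 (SE 0.0002) |
| MAP mean, SD and correlation varied within rounding | 0.257 to 0.261 |
| MAP correlation 0 | 0.254 |

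The correlation of 0 was tried because the Section 7.1 text says it was set to 0 and then reports −0.08. Every stated input gives a value above 0.25. Only inputs that the protocol does not state fall below it: a correlation of +0.08 (0.248) or the MAP component alone (0.239). The gap, 0.259 − 0.243 = 0.016, is the largest of the 37, and this is the only row whose current-dose value changes side of 0.25.

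**Step 4: could this be sampling error?** The scatter across the 37 rows is what about 3,000 effective draws would give. At that size the standard error is √(0.259 × 0.741 / 3,000) = 0.0080, so row 13 is off by 0.016 / 0.0080 = 2 standard errors. That is unremarkable for the largest of 37.

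**Step 5: scenarios 41 and 38.**

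| Scenario | Dose | P(target) | P(overdose) |
|---|---|---|---|
| 41 | 7 mg | 0.661 | 0.108 |
| 41 | 8 mg | 0.628 (printed 0.625) | 0.245 (printed 0.236) |
| 38 | 7 mg | 0.611 | 0.104 |
| 38 | 8 mg | 0.599 (printed 0.597) | 0.226 (printed 0.226) |

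Both doses meet EWOC in both rows, and P(target) is higher at 7 mg. The difference is 0.661 − 0.628 = 0.033 in row 41 (0.032 to 0.034 over rounding) and 0.611 − 0.599 = 0.012 in row 38. For noise to explain row 41, the 7 mg estimate would have had to fall below the printed 0.625, an error of 0.036. With a standard error of √(0.661 × 0.339 / 3,000) = 0.0086, that is about 4 standard errors. For row 38 it is 0.611 − 0.597 = 0.014 against √(0.611 × 0.389 / 3,000) = 0.0089, about 1.6.

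**The case against.** The strongest defence is that the rows are hypothetical. The model is re-run on actual data, the SMC weighs other safety information, and an illustrative row authorises no dose. That stands and limits the severity.

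Several stronger readings are tempting and should be resisted.

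- **That the row breaks the bar on escalation in Section 3.1.** That bar covers escalating to a dose that fails EWOC. In scenario 13 the current and next dose are both 6 mg. The conflict is with Section 7.1, which takes the recommended dose only from doses fulfilling EWOC, whether or not the dose changes.
- **That sampling error is established, and that live decisions will carry it.** No draw count is given, so the cause is inferred. The statement about R and JAGS concerns the scenarios and simulations already run, while the SAP names SAS 9.4 for all analyses. Gibbs updating is planned on trial, but the documents do not say with what code or chain length.
- **That the table is generally unreliable.** It is not: agreement is close in most of the 37 rows, and scenario 5, the closest to the limit, is reproduced.
- **That rows 38 and 41 are further numerical errors, or show the wrong dose.** Their 8 mg entries are nearly exact. In both rows P(target) exceeds 0.5, so the first criterion for the MTD is met, and 8 mg fits the MTD definition as the highest dose meeting EWOC. The rows may follow that definition instead of the next-cohort rule. The documents do not say which.

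**Conclusion.** The point holds, and should be fixed. Under the printed prior and model, scenario 13 has P(overdose) 0.259 at 6 mg, not 0.243, so the listed next dose does not meet the Section 7.1 limit. The error of 0.016 is small, but it crosses the decision threshold. It affects one row of the 37 that could be checked. The conclusion assumes that Table 7.1:2 is the prior actually used and that the likelihood is binomial; it survives rounding of the prior and the text's alternative correlation of 0. Monte Carlo error is the likely cause, not a demonstrated one.

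Separately, row 41 clearly, and row 38 marginally, depart from the highest-P(target) rule in Section 7.1 while remaining consistent with the MTD definition. A reader might conclude that these rows name the wrong dose; the documents support only that the two rules give different answers there.

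**What to change.** Compute the posterior by deterministic grid integration, which is easy with two parameters, for both the appendix and the on-trial updates. Alternatively, state a Monte Carlo precision for P(overdose) small enough to settle values near 0.25. As illustration, placing 0.259 two standard errors above 0.25 needs a standard error of 0.0045, or 0.259 × 0.741 / 0.0045² ≈ 9,500 effective draws. Placing 0.249 two standard errors below needs 0.0005, or 0.249 × 0.751 / 0.0005² ≈ 750,000. Integration is the simpler route.

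Regenerate Table 10.2:1 with that code. Reconcile row 13 with the EWOC limit. Reconcile rows 38 and 41 with both the Section 7.1 selection rule and the MTD definition, and state which of the two the table's next-dose column applies.

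The cost is a few hours of programming and a corrected appendix table, with no effect on timelines.

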### Operating characteristics

Operating characteristics are a way to assess the long-run behaviour of a model by illustrating the precision of the design in estimating the MTD. Under an assumed true dose-toxicity curve, metrics such as the probability of recommending a dose with true DLT rate in the target interval can be approximated via simulation. Table 10.2:2 describes 6 assumed true dose-toxicity scenarios which were used to assess the operating characteristics of the model. These scenarios reflect a wide range of possible cases as follows:

- Scenario 1: aligned with prior means
- Scenario 2: high-toxicity scenario
- Scenario 3: low-toxicity scenario
- Scenario 4: non-logistic dose-toxicity scenario
- Scenario 5: low-toxicity followed by high-toxicity
- Scenario 6: too-toxicity scenario

Table 10.2:2 Assumed true dose-toxicity scenarios

Scenario		Dose (mg)			
		4 mg	6 mg	7mg	8 mg
1: Prior	P(DLT)	0.147	0.224	0.272	0.329
2: High Tox		0.22	0.34	0.40	0.45
3: Low Tox		0.04	0.11	0.13	0.16
4: Non- Logistic		0.1	0.2	0.25	0.3
5: Low-High		0.04	0.2	0.40	0.45
*6:Too Tox		0.42	0.68	0.75	0.81

Bold numbers indicate true DLT rates in the target interval [0.16, 0.33].

\* For Scenario 6, 2mg dose with 32% true DLT probability was added to the simulation condition in order for the R package to run (which needs at least one provisional dose level with true DLT probability in the target range).

For each of these scenarios, 1000 trials were simulated. Each cohort consisted of 3 patients. It was then assessed how often a dose was declared as MTD with true DLT rate in the under-, targeted or over-dose range.

Furthermore, the average, minimum and maximum number of patients per trial and the average number of DLTs per trial are reported. Results are shown in [Table 10.2:3](#).

Table 10.2.3

Simulated operating characteristics

Scenario	% of trials declaring a MTD with true DLT rate in				# Patients	# DLTs
	under dose	target dose	overdose	Stopped	Mean (Min-Max)	Mean (Min-Max)
1	19.4	66.3	0	14.3	15.3 (3-33)	3.4 (1-9)
2	0	25.2	32.2	42.6	11.6 (3-30)	3.4 (1-11)
3	26.2	72.6	0	1.2	16.8 (3-42)	1.9 (1-7)
4	11.7	76.7	0	11.6	13.6 (3-33)	2.7 (1-9)
5	14.4	48.7	35.1	1.8	15.9 (3-36)	3.7 (1-11)
6	0	20.8	12.8	66.4	8.6 (3-24)	3.7 (2-12)

In Scenario 1, which reflects the case that the true dose-toxicity is aligned with prior means, 66.3% of the simulated trials declared the dose 4 mg as MTD with true DLT rate under the targeted dose range.

Scenario 2 (high-toxicity scenario) shows, that when the true DLT rate is high, i.e. the majority dose levels with true DLT rate above the target interval, The probability of observing a DLT at 6 mg is 0.34 and therefore very close to the upper bound of the target range. This accounts for 17.7% out of 32.2% where we declared a dose as MTD in the overdose interval. 42.6% of the trials were stopped without declaring a MTD since all dose levels were too toxic. This is an expected situation for a high-toxicity scenario.

Scenario 3 shows that when the true DLT rate is low, 72.6% of the simulated trials declared the dose 4 mg as MTD with true DLT rate under the targeted dose range, and 26.2% of the simulated trials declared a MTD in the underdose interval.

Scenario 4 represents a case where the assumed true dose-toxicity curve does not follow a logistic shape. In this scenario, 76.7% of trials declared MTDs with true DLT rate in the target interval, and only a few trials declared MTDs with true DLT rate in the underdose interval. This illustrates that the model is not sensitive to model misspecification.

Scenario 5 shows that when the true DLT rate is low-high, 48.7% of the simulated trials declared a dose as MTD with true DLT rate in the targeted dose range.

Scenario 6 shows that when the true DLT rate is super high, 66.4% of simulated trials stopped, since none of the doses is considered tolerable anymore. This is an expected situation for a super high-toxicity scenario.

Proprietary confidential information © 2020 Boehringer Ingelheim International GmbH or one or more of its affiliated companies

The mean patient numbers range from 8.6 patients (Scenario 6) to 16.8 patients (Scenario 3) and the maximum number of patients was 42. Therefore, the patient numbers are as expected and increase when moving away from the high-toxicity scenario.

By reviewing the metrics presented in [Table 10.2:3](#), it can be seen that the model is not sensitive to different scenarios of truth. In general, this model is conservative due to the overdose control criteria. In all scenarios, the probabilities of recommending a dose with true  $P(DLT) \geq 33\%$  as MTD are much smaller than probabilities of recommending a dose with true  $P(DLT)$  between 16% and 33% as MTD.

On-study recommendations based on the model are consistent with the clinical decision making process, and should be considered in conjunction with other available clinical information by the BI clinical trial team and trial investigators in deciding the dose levels to be tested in order to determine the MTD estimate.

R version 3.5.1 and JAGS were used for data scenarios and simulations.

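### Appendix 10.2 concludes that overdose selection is much smaller than target selection in all scenarios; Table 10.2:3 contradicts this, and two scenario sentences misreport the table

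*Protocol*

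**What the plan says.** Protocol 7.1 sets the target interval at 0.16 up to but not including 0.33, and calls 0.33 and above over-toxic. Appendix 10.2 gives six assumed true dose-toxicity curves (Table 10.2:2). From 1000 simulated trials per curve, Table 10.2:3 reports how often the declared MTD was below, in or above target, and how often the trial stopped without one.

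The closing paragraph reads the table as follows: "In all scenarios, the probabilities of recommending a dose with true" P(DLT) of 33% or more as MTD "are much smaller than probabilities of recommending a dose with true" P(DLT) between 16% and 33%. It adds "In general, this model is conservative due to the overdose control criteria" and "it can be seen that the model is not sensitive to different scenarios of truth".

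The scenario texts say:
- Scenario 1: "66.3% of the simulated trials declared the dose 4 mg as MTD with true DLT rate under the targeted dose range".
- Scenario 2, on 6 mg with a true rate of 0.34: "This accounts for 17.7% out of 32.2% where we declared a dose as MTD in the overdose interval".
- Scenario 3: "72.6% of the simulated trials declared the dose 4 mg as MTD with true DLT rate under the targeted dose range". The same sentence then gives 26.2% as the underdose share.
- Scenario 4: the curve is described as not logistic in shape, and the result is taken to show that the model is insensitive to misspecification.
- Scenario 5: "48.7% of the simulated trials declared a dose as MTD with true DLT rate in the targeted dose range". The overdose percentage is not mentioned.

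**The concern.** The appendix exists to show how precisely the design estimates the MTD, which is a primary endpoint, and Protocol 7.1 and 7.6 both refer the reader to it. A reader who takes the closing paragraph at its word will believe that an over-toxic dose is rarely declared compared with a target dose, whatever the truth. The table beside it says otherwise in one scenario and gives only modest gaps in two more.

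The Scenario 1 and 3 sentences mislead in the other direction. As printed, they say that the design settles on the lowest dose, below target, in about two thirds to three quarters of trials.

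At stake is the accuracy of the performance description, not the conduct of the trial.

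**Working it through.** **Inputs.** True DLT rates come from Table 10.2:2, selection percentages from Table 10.2:3, intervals from Protocol 7.1, and 1000 trials per scenario from Appendix 10.2. Each row of Table 10.2:3 sums to 100.0, so the table is internally consistent.

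**Step 1. Overdose against target selection.**

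| Scenario | Doses with true rate ≥ 0.33 | Under % | Target % | Overdose % | Stopped % | Overdose/target |
|---|---|---|---|---|---|---|
| 1 | none (highest 0.329) | 19.4 | 66.3 | 0 | 14.3 | 0 |
| 2 | 6, 7, 8 mg (0.34, 0.40, 0.45) | 0 | 25.2 | 32.2 | 42.6 | 1.28 |
| 3 | none (highest 0.16) | 26.2 | 72.6 | 0 | 1.2 | 0 |
| 4 | none (highest 0.30) | 11.7 | 76.7 | 0 | 11.6 | 0 |
| 5 | 7, 8 mg (0.40, 0.45) | 14.4 | 48.7 | 35.1 | 1.8 | 0.72 |
| 6 | 4 to 8 mg (0.42 to 0.81) | 0 | 20.8 | 12.8 | 66.4 | 0.62 |

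Overdose selection is impossible in Scenarios 1, 3 and 4. In Scenario 6 the only target dose is the 2 mg level (32%) added so that the software would run, so all 20.8 points are at 2 mg.

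**Step 2. Could simulation error explain it?** Let o and t be the overdose and target proportions. The Monte Carlo standard error of o − t is sqrt((o + t − (o − t)²)/1000).
- Scenario 2: 0.322 − 0.252 = +7.0 points; SE = sqrt((0.574 − 0.0049)/1000) = 2.39 points; 95% CI +2.3 to +11.7.
- Scenario 5: −13.6 points; SE 2.86; 95% CI −19.2 to −8.0.
- Scenario 6: −8.0 points; SE 1.82; 95% CI −11.6 to −4.4.

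For the ratio o/t, the SE of its logarithm is sqrt(1/(1000·o) + 1/(1000·t)). The 95% intervals are 1.08 to 1.51 (Scenario 2), 0.63 to 0.83 (Scenario 5) and 0.49 to 0.77 (Scenario 6). The Scenario 2 reversal is not simulation noise.

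**Step 3. How much rests on 6 mg in Scenario 2?** Counting 6 mg as target gives overdose 32.2 − 17.7 = 14.5% and target 25.2 + 17.7 = 42.9%. The order then reverses, with a ratio of 14.5/42.9 = 0.34. Scenario 5 has no such borderline dose.

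**Step 4. The Scenario 1 and 3 sentences.** In Scenario 1 the only dose below target is 4 mg (0.147), so 4 mg was declared in 19.4% of trials. The 66.3% is spread over 6, 7 and 8 mg, all in target. In Scenario 3 the only target dose is 8 mg (0.16), so 72.6% is selection of 8 mg. The doses 4, 6 and 7 mg together account for 26.2%, so 4 mg accounts for at most that.

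**Step 5. Is Scenario 4 non-logistic?** A least-squares fit of logit(p) on log(d/8) to 0.10, 0.20, 0.25, 0.30 gives intercept −0.84 and slope 1.95. The fitted rates are 0.1005, 0.1978, 0.2499 and 0.3018, with a largest error of 0.0022. That is smaller than two-decimal rounding (0.005), so the protocol's own model family describes this curve almost exactly.

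**The case against.** The strongest defence concerns Scenario 2. The reversal hinges on a dose with a true rate of 0.34, one point above the bound, and the protocol discloses its share exactly. This stands as context and belongs in any restatement. It does not rescue the sentence, which sets its own cut at 33% in line with Protocol 7.1. Nor does it touch Scenario 5.

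Second, whether 0.72 and 0.62 count as much smaller is a matter of wording, and the order in Scenarios 5 and 6 is as stated. This also stands: only Scenario 2 is a strict contradiction. But a claim covering all scenarios needs more than three scenarios where the event cannot occur.

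Third, the description of the design as conservative is hedged and has support in the table: 42.6% of trials stop in Scenario 2, 66.4% in Scenario 6 and 14.3% in Scenario 1, and 26.2% select below target in Scenario 3. This is fair.

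A reader might also infer that Scenario 5's 35.1% shows the model failing under misspecification, because that curve fits the logistic less well (largest error 0.055 in the same kind of fit, 0.038 at best). The documents do not show this, and a check points the other way. The BLRM was rebuilt from the Table 7.1:2 prior, with assumed stopping rules because the simulation's own rule is not printed. Selection of 7 or 8 mg under the true Scenario 5 curve, against its exactly logistic fit (0.041, 0.209, 0.345, 0.490), was 33.4% against 35.9% under a stricter rule and 41.0% against 41.6% under a looser one. A second pair of runs gave 36.0% against 37.2% and 44.2% against 45.4%. Overdose selection is about as high with no misspecification, so the steep rise between neighbouring doses is the likelier reason.

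**Conclusion.** The closing statement is wrong as written. Overdose selection is larger than target selection in Scenario 2 (by 7.0 points, 95% CI 2.3 to 11.7, with 6 mg classified by the protocol's own interval). It is 0.72 and 0.62 times as large in Scenarios 5 and 6, and zero only where no simulated dose is over-toxic. Two scenario sentences, for Scenarios 1 and 3, misreport the table. The Scenario 2, 4 and 5 percentages are quoted correctly: the Scenario 5 text is incomplete, and the Scenario 4 problem is one of label and inference. Scenario 4 is too close to logistic to support the misspecification conclusion.

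A reader might go further and infer that overdose control does not work or that the design is unsafe. The documents do not support that. The criterion limits the posterior probability that a dose is over-toxic; it does not limit how often such a dose is selected under one fixed true curve. Trials that stop without an MTD are part of its action. Model output is also weighed with other clinical information, and the SMC decides on dose levels.

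The main result rests only on printed figures and the stated 1000 trials per scenario. The Scenario 4 result adds one curve fit. No dose, decision rule or sample size depends on the sentences at issue.

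**What to change.** In Appendix 10.2:
- Replace the closing all-scenarios sentence with the overdose and target figures for Scenarios 2, 5 and 6 (32.2% vs 25.2%, 35.1% vs 48.7%, 12.8% vs 20.8%). Note the 17.7-point share at 6 mg in Scenario 2 and the added 2 mg dose in Scenario 6, and say that Scenarios 1, 3 and 4 cannot show overdose selection.
- Add the 35.1% overdose figure to the Scenario 5 text, without attributing it to misspecification.
- Restate 66.3% and 72.6% as target-interval selections (6 to 8 mg in Scenario 1, 8 mg in Scenario 3).
- Describe Scenario 4 as near-logistic and remove the misspecification conclusion drawn from it.

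The cost is a text edit from numbers already in Tables 10.2:2 and 10.2:3, with no rerun. The one downside is that the stated performance reads less favourably.
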